10.4 APPENDIX 4: CONTRACEPTIVE AND BARRIER GUIDANCE

10.4.1 Definitions

Woman of childbearing potential (WOCBP): A woman is considered fertile following menarche and until becoming post-menopausal unless permanently sterile (see below).

If fertility is unclear (eg, amenorrhea in adolescents or athletes) and a menstrual cycle cannot be confirmed before first dose of study intervention, additional evaluation should be considered.

Women in the following categories are not considered WOCBP

1. Premenarchal
2. Premenopausal female with 1 of the following:
 - Documented hysterectomy
 - Documented bilateral salpingectomy
 - Documented bilateral oophorectomy

For individuals with permanent infertility due to an alternate medical cause other than the above, (eg, mullerian agenesis, androgen insensitivity), Investigator discretion should be applied to determining study entry.

Note: Documentation can come from the site personnel's: review of the participant's medical records, medical examination, or medical history interview.

3. Postmenopausal female
 - A postmenopausal state is defined as no menses for 12 months without an alternative medical cause.
 - A high follicle stimulating hormone (FSH) level in the postmenopausal range may be used to confirm a postmenopausal state in women not using hormonal contraception or hormonal replacement therapy (HRT). However, in the absence of 12 months of amenorrhea, confirmation with more than one FSH measurement is required.

Females on HRT and whose menopausal status is in doubt will be required to use one of the non-estrogen hormonal highly effective contraception methods if they wish to continue their HRT during the study. Otherwise, they must discontinue HRT to allow confirmation of postmenopausal status before study enrollment

10.4.2 Contraception guidance

COLLECTION OF PREGNANCY INFORMATION:

Male participants with partners who become pregnant

- The Investigator will attempt to collect pregnancy information on any male participant's female partner who becomes pregnant while the male participant is in this study. This applies only to male participants who receive study intervention.
- After obtaining the necessary signed informed consent from the pregnant female partner directly, the Investigator will record pregnancy information on the appropriate form and submit it to the Sponsor within 24 hours of learning of the partner's pregnancy. The female partner will also be followed to determine the outcome of the pregnancy. Information on the status of the mother and child will be forwarded to the Sponsor. Generally, the follow-up will be no longer than 6 to 8 weeks following the estimated delivery date. Any termination of the pregnancy will be reported regardless of fetal status (presence or absence of anomalies) or indication for the procedure.

[figure not shown]
Female participants who become pregnant

- The Investigator will collect pregnancy information on any female participant who becomes pregnant while participating in this study. The initial information will be recorded on the appropriate form and submitted to the Sponsor within 24 hours of learning of a participant's pregnancy.
- The participant will be followed to determine the outcome of the pregnancy. The Investigator will collect follow-up information on the participant and the neonate and the information will be forwarded to the Sponsor. Generally, follow-up will not be required for longer than 6 to 8 weeks beyond the estimated delivery date. Any termination of pregnancy will be reported, regardless of fetal status (presence or absence of anomalies) or indication for the procedure.
- Any pregnancy complication or elective termination of a pregnancy for medical reasons will be reported as an AE or SAE.
- A spontaneous abortion (occurring at <22 weeks gestational age) or still birth (occurring at >22 weeks gestational age) is always considered to be an SAE and will be reported as such.
- Any post-study pregnancy related SAE considered reasonably related to the study intervention by the Investigator will be reported to the Sponsor as described in [Section 8.3.4](#). While the Investigator is not obligated to actively seek this information in former study participants, he or she may learn of an SAE through spontaneous reporting.

Any female participant who becomes pregnant while participating in the study will discontinue study intervention or be withdrawn from the study.

10.5 APPENDIX 5: LIVER AND OTHER SAFETY: SUGGESTED ACTIONS AND FOLLOW-UP ASSESSMENTS

NEUTROPENIA

[figure not shown]

3. **INFORM** the local monitor
4. **INVESTIGATE** previous treatments particularly long-term, even a long time ago, exposure to toxic agents, e.g., benzene, X-rays, etc.
5. **PERFORM** and collect the following investigations (results):
 - RBC and platelet counts, Absolute Neutrophil Count (ANC)
 - Infectious serologies to be performed locally, according to clinical symptoms / medical history
6. **DECISION** for bone marrow aspiration: to be taken in specialized unit
7. **COLLECT/STORE** one sample following handling procedures described in PK sections (**for studies with PK sampling**)
8. **MONITOR** the leukocyte count 3 times per week for at least one week, then twice a month until it returns to normal

* For individuals of African descent, the relevant value of concern is $<1000/\text{mm}^3$

[figure not shown]
Neutropenia is to be recorded as an AE only if at least 1 of the criteria listed in the general guidelines for reporting AEs is met.

THROMBOCYTOPENIA

Thrombocytopenia is to be recorded as an AE only if at least 1 of the criteria listed in the general guidelines for reporting AEs is met.

INCREASE IN ALT

*If unable to retest in 72 hours, use original lab results to decide on further reporting/monitoring/discontinuation.

[figure not shown]
Note:

“Baseline” refers to ALT sampled at baseline visit; or if baseline value unavailable, to the latest ALT sampled before the baseline visit. The algorithm does not apply to the instances of increase in ALT during screening.

See [Section 10.3](#) for guidance on safety reporting.

[figure not shown]
Normalization is defined as ≤ULN or baseline value, if baseline value is >ULN.

**INCREASE IN SERUM CREATININE in patients with normal baseline
(creatininemia between 45 µmol/L and 84 µmol/L)**

Increase in serum creatinine is to be recorded as an AE only if at least 1 of the criteria listed in the general guidelines for reporting AEs is met.

INCREASE IN CPK OF NON-CARDIAC ORIGIN AND NOT RELATED TO INTENSIVE PHYSICAL ACTIVITY

Increase in CPK is to be recorded as an AE only if at least 1 of the criteria in the general guidelines for reporting AEs is met.

10.6 APPENDIX 6: CONTINGENCY MEASURES FOR A REGIONAL OR NATIONAL EMERGENCY THAT IS DECLARED BY A GOVERNMENTAL AGENCY

Continuation of the study in the event of a regional or national emergency declared by a governmental agency:

A regional or national emergency declared by a governmental agency (eg, public health emergency, natural disaster, pandemic, terrorist attack) may prevent access to the clinical trial site.

Contingency procedures are suggested below and in sections for an emergency that prevents access to the study site, to ensure the safety of the participants, to consider continuity of the clinical study conduct, protect trial integrity, and assist in maintaining compliance with Good Clinical Practice in Conduct of Clinical Trials Guidance. Sponsor agreement **MUST** be obtained prior to the implementation of these procedures for the duration of the emergency.

During the emergency, if the site will be unable to adequately follow protocol mandated procedures, alternative treatment outside the clinical trial should be proposed, and screening/enrollment/randomization/administration of study intervention may be [temporarily delayed/halted].

Attempts should be made to perform all assessments in accordance with the approved protocol to the extent possible. In case this is not possible due to a temporary disruption caused by an emergency, focus should be given to assessments necessary to ensure the safety of participants and those important to preserving the main scientific value of the study.

Procedures to be considered in the event of a regional or national emergency declared by a governmental agency:

- If onsite visits are not possible, remote visits (eg, with home nurses, home health vendor, etc.) may be planned for the collection of possible safety and/or efficacy data.
- If onsite visits are not possible visit windows may be extended for assessment of safety and/or efficacy data that cannot be obtained remotely.
- Use of local clinic or laboratory locations may be allowed.

Informed consent: For a regional or national emergency declared by a governmental agency, contingency procedures may be implemented for the duration of the emergency. The participants or their legally authorized representative should be verbally informed prior to initiating any changes that are to be implemented for the duration of the emergency (eg. study visit delays/treatment extension, use of local labs).

- Contingencies implemented due to emergency will be documented.

10.7 APPENDIX 7: ABBREVIATIONS

| | |
|--------|--|
| AEs: | adverse events |
| AESIs: | adverse events of special interest |
| DTP: | direct-to-patient |
| ICF: | informed consent form |
| IMPs: | investigational medicinal products |
| NIMPs: | non-investigational medicinal products |
| NMPA: | National Medical Products Administration |
| PCSA: | potentially clinically significant abnormality |
| SAEs: | serious adverse events |
| SMPG: | self-monitored plasma glucose |
| SUSAR: | suspected unexpected serious adverse reaction |

10.8 APPENDIX 8: PROTOCOL AMENDMENT HISTORY

The Protocol Amendment Summary of Changes Table for the current amendment is located directly before the Table of Contents (TOC).

3.4 TERTIARY/EXPLORATORY ENDPOINT(S) ANALYSIS.....	20
3.5 MULTIPLICITY ISSUES	20
3.6 SAFETY ANALYSES	21
3.6.1 Extent of exposure	21
3.6.2 Adverse events	22
3.6.3 Additional safety assessments.....	25

3.6.3.1	Laboratory variables, vital signs and electrocardiograms (ECGs).....	25
3.6.3.2	Analysis of hypoglycemia.....	27
3.7	OTHER ANALYSES	28
3.7.1	Other variables and/or parameters	28
3.7.2	Subgroup analyses	28
3.8	INTERIM ANALYSES	29
4	SAMPLE SIZE DETERMINATION	30
5	SUPPORTING DOCUMENTATION	31
5.1	APPENDIX 1 LIST OF ABBREVIATIONS	31
5.2	APPENDIX 2 PARTICIPANT DISPOSITIONS	31
5.3	APPENDIX 3 DEMOGRAPHICS AND BASELINE CHARACTERISTICS, PRIOR OR CONCOMITANT MEDICATIONS	32
5.4	APPENDIX 4 DATA HANDLING CONVENTIONS	34
5.5	APPENDIX 5 DEFINITION AND MEDICAL ALGORITHM FOR "RESCUED PARTICIPANTS" / RESCUE MEDICATION USE	35
5.6	APPENDIX 6 CRITERIA FOR POTENTIALLY CLINICALLY SIGNIFICANT ABNORMALITIES	36
5.7	APPENDIX 7 PRE-DEFINED PROTOCOL DEVIATIONS AND CATEGORIZATION	41

LIST OF TABLES

Table 1 - Objectives and endpoints.....	6
Table 2 - Summary of primary estimand for main endpoints	8
Table 3 - Populations for analyses	11
Table 4 - Sorting of AE tables	23
Table 5 - Analyses of adverse events	24
Table 6 - Selections for AESIs	25
Table 7 - Analyses window definition for HbA1c and body weight.....	35

LIST OF FIGURES

Figure 1 - Graphical illustration of the gate-keeping procedure	21
---	----

VERSION HISTORY

This statistical analysis plan (SAP) for study LPS17396 is based on the amended protocol 01 dated 16 June 2022. There are no major changes to the statistical analysis features in this SAP.

The first participant was randomized on 18 July 2022.

Major changes in statistical analysis plan

SAP Version	Approval Date	Changes	Rationale
1	14-Nov-2023	For the other secondary endpoint “total insulin dose in each group at Week 24”, estimand attributes were added in this SAP.	The details of estimand were not defined in protocol. Estimand attributes were added following team’s decision.

1 INTRODUCTION

There are no major changes to the analyses described in the protocol.

1.1 STUDY DESIGN

- Open-label, 1:1 randomized, active-controlled, 2 treatment-arm, 24-week treatment duration, parallel-group, multicenter phase 3 study
- Participants with type 2 diabetes mellitus (T2DM) treated with metformin ± one additional oral antidiabetic drug (OAD) would be recruited in this study.
- The randomization will be stratified by value of screening HbA1c (<8%, ≥8%), and by use at screening of metformin alone or metformin + SGLT-2i (Yes/No), ie, by oral antidiabetic treatment use at screening (metformin ± SGLT-2i / metformin + OAD other than SGLT-2i). The overall objective of this last stratification group is to ensure that participants who will need to discontinue their second OAD are well balanced between groups
- Total duration of study participation for each participant is up to 27 weeks.
- This study comprises of 3 periods:
 - An up-to 2-week screening period during which: a sulfonylurea (SU), a glinide, an alpha-glucosidase inhibitor (alpha-GI), or a dipeptidyl-peptidase-4 (DPP-4) inhibitor, if previously taken, will be discontinued. Sodium-glucose co-transporter 2 (SGLT-2) inhibitor, if previously taken, will be kept at the stable dose; metformin treatment will maintain at the stable dose (at least 1000 mg/day or a maximal tolerated dose).
 - A 24-week, open-label randomized treatment period with iGlarLixi or IDegAsp, both on top of metformin ± SGLT-2 inhibitor.
 - A 3-day post-treatment safety follow-up period.
- Screening is from signed informed consent to randomization.

1.2 OBJECTIVES AND ENDPOINTS

Table 1 - Objectives and endpoints

Objectives	Endpoints
Primary	

• To demonstrate the non-inferiority of iGlarLixi versus IDegAsp on glycated hemoglobin A1c (HbA1c) change from baseline to Week 24	
• Change in HbA1c from baseline to Week 24
Key secondary efficacy	
• 2a Change in HbA1c from baseline to Week 24• 2b Change in body weight from baseline to Week 24

Objectives	Endpoints
HbA1c target, proportion of participants at target without weight gain and/no hypo after 24 weeks of treatment	
2c Proportion of participants to reach HbA1c<7% at week 242d Proportion of participants reaching HbA1c targets <7% without body weight gain at Week 242e Proportion of participants reaching HbA1c <7% with no body weight gain at Week 24 and no hypoglycemia (defined as ADA level 1,2 or 3) during treatment
Other secondary	
Change in fasting plasma glucose from baseline to Week 24Change in 7-point self-monitored plasma glucose (SMPG) profile from baseline to Week 24 (each time point and average daily value)Proportion of participants reaching HbA1c target <7% at Week 24 with no hypoglycemia (defined as ADA level 1, 2 or 3) during treatmentProportions of participants reaching HbA1c target <7% at Week 24 with no clinically relevant hypoglycemia (defined as ADA level 2 or 3) during treatmentTotal insulin dose in each group at Week 24Percentage of participants requiring rescue therapy during the 24-week treatment periodChange in fasting C-peptide from baseline to Week 24
Secondary Safety	
To assess safety and tolerability of iGlarLixi versus IDegAspIncidence and event rates of hypoglycemia (Any, ADA classification level 1, 2, and 3)Adverse events (AEs), serious adverse events (SAEs), adverse events of special interest (AESIs), and AEs leading to treatment discontinuation, vital signs and safety laboratory values

1.2.1 Estimands

Primary estimand defined for main endpoints are summarized in below [Table 2](#). More details are provided in [Section 3](#).

For all these estimands, the comparison of interest will be the comparison of iGlarLixi vs. IDegAsp.

Table 2 - Summary of primary estimand for main endpoints

Endpoint Category (estimand)	Estimands			
	Endpoint	Population	Intercurrent event(s) handling strategy	Population-level summary (Analysis and missing data handling)
Primary objective: To demonstrate the non-inferiority of iGlarLixi versus IDegAsp on glycated hemoglobin A1c (HbA1c) change from baseline to Week 24				
Primary endpoint (Primary estimand)	Change in HbA1c from baseline to Week 24 ^a	All randomized participants	Treatment policy strategy for both intercurrent events: 
 • Treatment discontinuation • Initiation of rescue medication 	LS Means difference between treatments. Multiple imputation of missing data using missingness patterns based on treatment completion, and under the missing at random (MAR) assumption within each pattern.
Primary endpoint (Secondary estimand 1)	Change in HbA1c from baseline to Week 24 ^a	All randomized participants	Hypothetical strategy for both intercurrent events: 
 • Treatment discontinuation • Initiation of rescue medication 	LS Means difference between treatments. Missing data handled by mixed-effect model with repeated measures (MMRM) under MAR assumption.
Primary endpoint (Secondary estimand 2)	Change in HbA1c from baseline to Week 24 ^a	Per Protocol	No intercurrent event expected as participants with treatment discontinuation or rescue medication will be excluded from PP population	LS Means difference between treatments. No missing data handling method is planned for this analysis.
Key secondary efficacy objective: To demonstrate superior therapeutic effect of iGlarLixi versus IDegAsp on HbA1c and body weight change, proportion of participants at HbA1c target, proportion of participants at target without weight gain and/no hypo after 24 weeks of treatment				

Endpoint Category (estimand)	Estimands				
	Endpoint	Population	Intercurrent event(s) handling strategy	Population-level summary (Analysis and missing data handling)	
Key secondary efficacy endpoint (Primary estimand)	Change from baseline to Week 24 in: 
 • HbA1c^b • Body weight 	All randomized participants	Treatment policy strategy for both intercurrent events: 
 • Treatment discontinuation • Initiation of rescue medication 	LS mean difference between treatments. Multiple imputation of missing data using missingness patterns based on treatment completion, and under the MAR assumption within each pattern.	Odds ratio between treatments. If no assessment is available at Week 24, participants will be treated as non-responders.
	If a participant achieves: 
 • HbA1c < 7% at Week 24 • HbA1c < 7% and no body weight gain at Week 24 • HbA1c < 7% and no body weight gain at Week 24 and no hypoglycemia (defined as any hypoglycemia ADA level 1, 2 or 3) during treatment 	All randomized participants	Treatment policy strategy for both intercurrent events: 
 • Treatment discontinuation • Initiation of rescue medication 		
Key secondary efficacy endpoint (Secondary estimand)	Change from baseline to Week 24 in: 
 • HbA1c^b • Body weight 	All randomized participants	Hypothetical strategy for both intercurrent events: 
 • Treatment discontinuation • Initiation of rescue medication 	LS Means difference between treatments. Missing data handled by MMRM under MAR assumption.	
Other secondary objectives: To further assess the therapeutic effect of iGlarLixi in comparison with IDegAsp on other glycemic control parameters after 24 weeks of treatment. To assess total insulin dose and percentage of participants requiring rescue therapy over the 24 weeks treatment					
Other secondary endpoints (Primary estimand)	Change from baseline to Week 24 in: 
 • FPG • 7-point SMPG • Fasting C-peptide 	All randomized participants	Treatment policy strategy for both intercurrent events: 
 • Treatment discontinuation • Initiation of rescue medication 	LS mean difference between treatments. Multiple imputation of missing data using missingness patterns based on treatment completion, and under the MAR assumption within each pattern.	

Endpoint Category (estimand)	Estimands			
	Endpoint	Population	Intercurrent event(s) handling strategy	Population-level summary (Analysis and missing data handling)
If a participant achieves:				
	
 • HbA1c < 7% at Week 24 and no hypoglycemia (any hypoglycemia ADA level 1, 2 or 3) during treatment • HbA1c < 7% at Week 24 and no clinically relevant hypoglycemia (any hypoglycemia ADA level 2 or 3) during treatment 	All randomized participants	
Treatment policy strategy for both intercurrent events:
 
 • Treatment discontinuation • Initiation of rescue medication 	Odds ratio between treatments. If no assessment is available at Week 24, participants will be treated as non-responders.
If a participant initiates rescue medication by Week 24		All randomized participants	
Treatment policy strategy for intercurrent event:
 
 • Treatment discontinuation^c 	Odds ratio between treatments. If no assessment is available at Week 24, participants will be treated as non-responders.
Total insulin dose in each group at Week 24		All randomized participants	
Treatment policy strategy for intercurrent event:
 
 • Initiation of rescue medication 
Hypothetical strategy for intercurrent event:
 
 • Treatment discontinuation 	LS Means difference between treatments. Missing data handled by mixed-effect model with repeated measures (MMRM) under MAR assumption.

a For noninferiority testing.

b For superiority testing.

c Initiation of rescue medication is not applicable for this estimand.

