6.8.4 Rescue medicine

The date and time of rescue medication administration as well as the name and dosage regimen of the rescue medication must be recorded.

Routine central laboratory alerts on HbA1c are required to ensure that glycemic parameter results remain under predefined threshold value. In case HbA1c is above threshold ($\text{HbA1C} > 8\%$ at Week 12 or later on), the investigator will receive an alert issued by the central laboratory and should ensure that no reasonable explanation exists for insufficient glucose control and in particular that the study treatment is appropriately titrated according to the titration algorithm (up to a maximum of 40 dose steps [40 U insulin glargine / 20 μg lixisenatide] for iGlarLixi group; no upper limit for IDegAsp group), compliance to diet and lifestyle is appropriate, and there is no intercurrent disease, which may jeopardize glycemic control (eg, infectious disease)

If any of the above can reasonably explain insufficient glycemic control, the Investigator should take appropriate actions and retest the central lab HbA1C in 4 weeks at next visit or an unscheduled visit whichever suitable.

If the repeated HbA1c remains above 8% despite appropriate corrective actions or none of the above-mentioned reasons can be found and managed, a rescue therapy can be considered.

- For iGlarLixi group, rescue therapy can be considered if a daily dose >40 dose steps is necessary to decrease HbA1c below the threshold, or if any safety concerns (repeated hypoglycemia, severe gastrointestinal AE, etc) prevent up titration to reach 40 dose steps according to the Investigator's judgment.
- In both iGlarLixi and IDegAsp treatment groups, it is recommended to add one rapid/short-acting insulin; this should be started as a single daily administration to be given at a meal of the day as appropriately at the investigator's discretion.

No other GLP-1 RA or DPP-4 inhibitor or basal insulin, including pre-mixed insulin, should be used as rescue medication in either of the treatment groups.

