Once rescue medication is considered as necessary as per the investigator's medical decision, the participant should be scheduled for a **Pre-rescue onsite visit**. Before initiating rescue therapy, all assessments (except 7-point SMPG) planned at the end of treatment visit are to be performed at the pre-rescue visit. After these assessments are completed and rescue therapy initiated, the participant will remain in the study and continue to administer the study treatment (including background therapies). The planned visits and assessments should be performed until the last scheduled visit.

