treatment group will be provided, as well as the odds ratio between groups with associated 2-sided CI at the specified significance level. For the categorical secondary endpoints in which HbA1c is assessed at Week 24, all values at Week 24 will be used to determine whether a participant is a responder or not, even if they are measured after IMP discontinuation or introduction of rescue therapy. If no assessment is available at Week 24, participants will be treated as non-responders. Details of the logistic model will be discussed in the SAP.

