3.3.2 Other secondary endpoints

3.3.2.1 *Definition of endpoints*

The other secondary endpoints are:

- Change in fasting plasma glucose from baseline to Week 24
- Change in 7-point self-monitored plasma glucose (SMPG) profile from baseline to Week 24 (each time point and average daily value)
- Proportion of participants reaching HbA1c target <7% at Week 24 with no hypoglycemia (defined as ADA level 1, 2 or 3) during treatment
- Proportions of participants reaching HbA1c target <7% at Week 24 with no clinically relevant hypoglycemia (defined as ADA level 2 or 3) during treatment
- Total insulin dose in each group at Week 24, defined as the sum of the insulin dose in U and U/kg from IMP and NIMP (eg, rescue therapy).
- Percentage of participants requiring rescue therapy during the 24-week treatment period
- Change in fasting C-peptide from baseline to Week 24

3.3.2.2 *Main analytical approach*

The other secondary endpoints of will be analyzed with the primary estimand defined according to the following attributes:

- Treatment condition: iGlarLixi will be compared to IDegAsp.
- Analysis population: All randomized participants for all endpoints, and additionally safety population for total insulin dose.
- Intercurrent events (IE):

- For total insulin dose in each group at Week 24
 - Treatment discontinuation IE will be handled with the hypothetical strategy: the endpoint will be considered as missing after treatment discontinuation
 - The initiation of rescue medication IE will be handled with the treatment policy strategy: the endpoint will be assessed based on all assessments irrespective of the initiation of rescue medication
- For percentage of participants requiring rescue therapy during the 24-week treatment period
 - Treatment discontinuation IE will be handled with the treatment policy strategy: the endpoint will be assessed based on all assessments irrespective of the treatment discontinuation
- For other endpoints:
 - Both treatment discontinuation IE and initiation of rescue medication IE will be handled with the treatment policy strategy: the endpoint will be assessed based on all assessments irrespective of the IE
- Population-level summary:

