 - For change in FPG, 7-point SMPG and fasting C-peptide from baseline to Week 24: LS Means difference between treatments from ANCOVA with the same analysis approach as of the primary estimand of the primary endpoint, except that the baseline of each endpoint will be included in the model rather than baseline HbA1c. Descriptive statistics for results and changes from baseline will be provided for baseline and each visit by treatment group. Mean changes from baseline with the corresponding standard error will be plotted over time. For 7-point SMPG, the average and each time point will be analyzed.
 - For total insulin dose in each group at week 24: LS mean difference between treatments, as well as SE and 2-sided 95% CI, from MMRM with treatment, randomization stratum of HbA1c, randomization stratum of previous OADs, visits and treatment-by-visit interaction as fixed effects. Descriptive statistics for percentage change from starting dose will be provided. Raw data and changes from starting dose with the corresponding standard error will be plotted over time.
 - For binary endpoints: Odds ratio between treatments from logistic regression model adjusting for treatment group, randomization stratum of previous OADs, baseline continuous HbA1c and appropriate baseline covariates. The proportion of participants in each treatment group will be provided, as well as the odds ratio between groups with associated 2-sided 95% CI. For the categorical secondary endpoints in which HbA1c is assessed at Week 24, all values at Week 24 will be used to determine whether a participant is a responder or not, even if they are measured after IMP discontinuation or introduction of rescue therapy. If no assessment is available at Week 24, participants will be treated as non-responders.

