Unscheduled visit measurements of laboratory data and vital signs will be used for computation of baseline, the last on-treatment value, analysis according to PCSAs, and the shift summaries for safety. They will also be included in the by-visit summaries if they are re-allocated to scheduled visits.

5.5 APPENDIX 5 DEFINITION AND MEDICAL ALGORITHM FOR “RESCUED PARTICIPANTS” / RESCUE MEDICATION USE

Participants who meet one of the following conditions will be considered as “rescued”:

- In the eCRF page “Medications”, if there is any medication with “Rescue Therapy” ticked for “Reason for Treatment”.
- In the eCRF page “Medications”, if there is no medication with “Rescue Therapy” ticked for “Reason for Treatment” and the participant meets any of the criteria in medical algorithm for rescued participants, defined as below.

Medical algorithm for rescued participants

- Short/rapid-acting insulin is given for > 10 days continuously, or ≤ 10 days continuously if it occurs within 2 weeks prior to the last HbA1c measurement.
- New OAD is taken in addition to metformin+/- SGLT-2i (identified from eCRF page “Medications”) > 10 days continuously, or ≤ 10 days continuously if it occurs within 2 weeks prior to the last HbA1c measurement.
- The dose of background therapy is increased for > 10 days continuously, or ≤ 10 days continuously if it occurs within 2 weeks prior to the last HbA1c measurement.

Nevertheless, the participants must not be considered rescued if:

- The date of anti-diabetic initiation is on or after the date of last IMP injection.
- The date of anti-diabetic initiation is before Week 12.
- The anti-diabetic medication was taken due to IMP unavailability during COVID-19 pandemic.

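### The rescue-therapy row of SAP Table 2 carries an HbA1c missing-data rule that can override dated rescue records

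*SAP*

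**What the plan says.** SAP Table 2 has a separate row for the endpoint "If a participant initiates rescue medication by Week 24". The row was adapted to this endpoint. Protocol 9.3.3.2 listed both intercurrent events for it, whereas footnote c of Table 2 removes rescue and leaves treatment discontinuation under a treatment policy strategy. The missing-data cell nevertheless has the same sentence as the HbA1c responder row above it: "If no assessment is available at Week 24, participants will be treated as non-responders".

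SAP 3.3.2.2 repeats the rule under its bullet for binary endpoints, without exempting rescue. There it follows a sentence that opens "For the categorical secondary endpoints in which HbA1c is assessed at Week 24". Protocol 9.3.3.1 has the same sequence, opening "For the categorical secondary endpoints in which HbA1c is assessed at Week 24, all values at Week 24 will be used".

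Rescue status itself is defined elsewhere. Protocol 6.8.4 lists "The date and time of rescue medication administration" among the items that must be recorded. SAP 5.5 (Appendix 5) begins "Participants who meet one of the following conditions will be considered as" rescued, and then works from the Medications eCRF page and a medical algorithm based on the timing of medication. It lists three exclusions: a drug started on or after the day of the final IMP injection, a drug started before Week 12, and use caused by IMP being unavailable during the COVID-19 pandemic.

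**The concern.** The other endpoints under this rule need an HbA1c value at Week 24, so a missing value leaves the outcome undetermined and a default is needed. Rescue accrues over the treatment period. A participant rescued at Week 15 who then misses Week 24 has a complete positive record: Appendix 5 classifies that person as rescued, and a missing Week 24 assessment is not among its exclusions. Table 2 as written can reverse that classification.

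The term non-responder is also undefined for an unfavourable event. It could mean that the event in the row was not met (not rescued) or that treatment failed (rescued). Two programmers could follow the same sentence and report different rescue proportions and odds ratios from the same data.

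**Working it through.** **Inputs.** The plan gives no rescue rate and no figure for this endpoint, so there is no plan result to reproduce. From SAP section 4: N = 290 per arm and a dropout rate of 10%. That sample size reproduces closely: 2 × (1.960 + 1.282)² × 1.05² / 0.3² gives 258 per arm; 258 / 0.9 gives 287, or 574 in total, against 580 stated.

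The rest is assumed:
- w = 10% have no Week 24 assessment (borrowing the dropout rate).
- r = true recorded rescue of 5%, 10% or 15%.
- e = share of the missing who left before Week 12 (0, 1/3 or 2/3). They cannot be recorded rescues, because Appendix 5 counts nothing before Week 12.
- Among those still present at Week 12, rescue and missingness are independent.

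**Formulas.**
- Probability of no Week 24 assessment, given presence at Week 12: q = w(1 − e) / (1 − we).
- Non-responder = not rescued: recorded rescues lost = N·r·q; reported proportion = r(1 − q).
- Non-responder = failure: never-rescued participants coded as rescued = N·w − N·r·q; reported proportion = r + w − r·q.

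**Counts per arm.**

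| e | q | Rescues lost at r = 5% / 10% / 15% | Reported (not rescued), r = 10% | Wrongly coded rescued, r = 10% | Reported (failure), r = 10% |
|---|---|---|---|---|---|
| 0 | 0.1000 | 1.45 / 2.90 / 4.35 | 9.00% | 26.1 | 19.0% |
| 1/3 | 0.0690 | 1.00 / 2.00 / 3.00 | 9.31% | 27.0 | 19.3% |
| 2/3 | 0.0357 | 0.52 / 1.04 / 1.55 | 9.64% | 28.0 | 19.6% |

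**If independence fails.** At r = 10% there are 29 rescues per arm. If 20% of rescued participants lacked a Week 24 assessment, 29 × 0.20 = 5.8 would be lost, twice the largest 10% figure in the table.

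**Odds ratio, equal missingness.** Take true rescue of 5% versus 10%: (0.05/0.95) / (0.10/0.90) = 0.474.
- Not rescued, e = 0: (0.045/0.955) / (0.09/0.91) = 0.476. The other values of e give 0.476 and 0.475.
- Failure, e = 0: (0.145/0.855) / (0.19/0.81) = 0.723. The other values of e give 0.718 and 0.712.

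**Odds ratio, unequal missingness.** Take true rescue of 5% in both arms (OR 1.00), 12% versus 8% missing, and e = 0.
- Not rescued: 0.88 × 0.05 = 0.044 and 0.92 × 0.05 = 0.046. OR = (0.044/0.956) / (0.046/0.954) = 0.95.
- Failure: 0.044 + 0.12 = 0.164 and 0.046 + 0.08 = 0.126. OR = (0.164/0.836) / (0.126/0.874) = 1.36.

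**The case against.** The best defence is that nobody would apply the rule this way. SAP 1.2.1 calls Table 2 a summary and sends the reader to Section 3 for detail. In Section 3.3.2.2 the rule follows a sentence about Week 24 HbA1c endpoints, and the same section gives separate intercurrent-event handling under "For percentage of participants requiring rescue therapy during the 24-week treatment period". On this view the sentence is an editorial leftover. That is a fair account of how it got there, but it does not remove the rule: the Table 2 cell belongs to the rescue row and has no HbA1c limitation, and Section 3.3.2.2 does not withdraw the rule for rescue.

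The second defence is that not rescued is the natural meaning, so the effect is small. This largely stands. Under that meaning never-rescued participants are coded exactly as under the proposed fix. Rescue generally requires HbA1c above 8% at Week 12 or later, sometimes after a four-week retest, so little time remains in which to drop out. Protocol 6.8.4 also says that after rescue starts "the participant will remain in the study and continue to administer the study treatment". The loss is nil, however, only if every rescued participant has a Week 24 assessment, which the plan cannot guarantee.

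Third, rescue status is not fully known for everyone. Appendix 5 closes the rescue period at the final IMP injection, so status is settled for someone who stopped IMP early with complete medication records to that point. For someone lost to follow-up after Week 12 while still on IMP, later rescue is unobserved. That stands, and the fix has to acknowledge it.

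**Conclusion.** The point holds as a minor error on one other secondary endpoint. Applied as written, the rescue row miscodes some participants: recorded rescues are dropped on the ordinary reading, or never-rescued participants become events on the less natural one. At an assumed 10% rescue and 10% missing, with independence, that is about 1 to 3 or about 26 to 28 per arm.

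Three stronger conclusions might be inferred, and the documents do not support them.
- **That the rescue proportion would nearly double.** This needs non-responder to mean rescued, which no sentence in the SAP says and which cuts against Appendix 5's positive criteria.
- **That the odds ratio is biased in a fixed direction, or is safe on the ordinary reading.** With equal missingness a true 0.47 becomes about 0.48 or 0.72; with 12% versus 8% missing a true 1.00 becomes 0.95 or 1.36. The direction depends on the reading and on the balance of missingness.
- **That 2.9 lost rescues per arm is a ceiling at 10% rescue.** It depends on independence.

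All rescue and missingness rates here are assumptions. The 10% is a sample-size dropout allowance, and participants who stop IMP are meant to be followed to scheduled completion, so the share without a Week 24 assessment may differ. The primary and key secondary analyses are unaffected, and the endpoint lies outside the hierarchical procedure in SAP 3.5.

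**What to change.** - Delete the missing-assessment sentence from the rescue row of SAP Table 2.
- State in SAP 3.3.2.2 that the sentence applies only to binary endpoints that use Week 24 HbA1c.
- Derive rescue status from Appendix 5, with its three exclusions, for all randomized participants. Count every qualifying record whether or not a Week 24 assessment exists.
- Code participants with no qualifying record as not rescued, and say that this is a convention for those lost to follow-up after Week 12 while still on IMP.

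The cost is two wording edits in the SAP, including the convention, and a check of the derivation code before database lock. No new data are needed, and the sample size does not change.
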